12.0 POTENTIAL RISKS

Potential adverse events that may occur and/or require treatment with use of the VIG include but are not limited to:

- allergic reaction to device materials or procedure medications
- anastomotic disruption or tearing
- aneurysm
- artery tear or rupture
- bleeding
- bruising
- contrast dye reaction
- death
- device breakage
- dissection or ‘tissue flap’ in blood vessels in which the VIG has been inserted
- embolism
- hematoma
- infection
- inflammation
- kinking/compression of the AVG and/or VIG device
- migration or misplacement of VIG device
- occlusion
- pseudoaneurysm in the AVG, VIG device, or adjacent native blood vessels
- seroma
- stenosis of the AVG
- swelling of implanted arm
- thrombosis of the AVG
- vessel spasm

Many of the potential adverse events listed above are similar to those that can occur during and after AVG placement using standard surgical techniques. Potential risks of a standard surgical procedure to implant an AVG for hemodialysis include but are not limited to the following:

- failure of sutures
- bleeding immediately after the procedure
- infection

- possible need for re-operation

The VIG will be used together with a standard 6mm AVG for hemodialysis that is sold and packaged separately. Potential adverse events that may occur with use of the AVG are described in the Instructions for Use packaged with the AVG.

Pregnant subjects are excluded from the study. In females of reproductive capacity, a pregnancy test must be performed prior to the procedure. This is to ensure that a fetus is not irradiated. Other potential risks to a fetus related to the study procedure are unknown.

There are no unique blood tests required for the study; however, results of standard blood tests performed to evaluate general health status at baseline, during the study procedure and during study follow-up will be included with the study data. Risks of having blood drawn include infection (rare) and bleeding (rare).

Steps to Minimize Risk

The following steps will be taken to minimize potential risks:

- Rigorous technical training will be provided to physician investigators that will perform the study procedures.
- On-site monitoring will occur during the first procedure at each site. On- site monitors will include a clinical representative of the sponsor. On-site monitors may also attend additional procedures throughout the course of the study.
- The study procedure will be performed in a surgical suite with radiologic imaging capabilities. In the event that the study procedure is unable to be performed (not expected), the patient will be able to receive traditional surgical graft implantation.

13.0 POTENTIAL BENEFITS

Potential clinical benefit(s) for the VIG are unknown at this time. Anastomoses with the VIG may potentially reduce venous vessel trauma, improve the local vessel wall shear stresses and promote laminar flow, thereby improving patency.

14.0 SUBJECT WITHDRAWAL FROM THE STUDY

Subjects may withdraw consent from the study at any time. Study data collected prior to withdrawal will be analyzed and included with the final study results. The investigator may withdraw the Subject from the study at any time if assessed to be in the best interest of the subject.

15.0 CRITERIA FOR STUDY TERMINATION

The study may be terminated at any time for reasons of safety, based on a recommendation by the IRB, the study DSMB, or based on other considerations by the Sponsor. Serious, device-related or possibly related adverse events that are unexpected in either frequency or type may prompt a review by the principal investigator, DSMB,

Medical Monitor and/or Sponsor, and may lead to consideration of stopping the study. Such a review and discussion will be documented and included with the study records.

16.0 STUDY DURATION

Enrollment is expected to occur over a 24-month period. The 6-month follow-up and 2-month period of data analysis and regulatory submission preparation is anticipated to be completed by Q2 of 2021.

17.0 TRAINING

The training of appropriate clinical site personnel will be the responsibility of Phraxis Clinical Department or their designees [e.g. Data Coordinating Center (DCC) staff]. To assure uniform data collection and protocol compliance, trainers will present a formal educational session to review the Investigational Plan, techniques for the identification of eligible subjects, instructions on data collection, follow-up schedules and regulatory requirements. Ongoing detailed email and telephone feedback regarding completion of CRFs will be provided by the DCC and through site monitoring to be performed by Phraxis representatives or their designee.

Prior to enrollment start, technical training on use of the study devices will be provided by a Sponsor representative, who may also attend/observe the roll-in cases. As part of the technical training, physician operators will also perform ‘test deployments’ of the study devices using a simulated-use model.

Roll-in Cases

Roll-in cases will be performed at each study site in order to confirm proper training and use of the study device and confirm comprehension of the study protocol. “Roll-in” subjects will be identified as such before enrollment and treated according to the same protocol and 6 month follow-up duration as used in the main study. Data from roll-in cases will be recorded using the same CRF as the main study. The number of roll-in cases per each site investigator will be determined by the Sponsor, in collaboration with the primary investigator at each site. No more than 1-2 roll-in cases per investigator are anticipated. The clinical experience and procedural data from roll-in cases will be reviewed by the Sponsor, in collaboration with each site investigator. Upon successful completion of the roll-in case requirements, as determined by the Sponsor, sites will be permitted to begin enrollment in the main study. Clinical data from roll-in cases will not be included in the primary study analysis but will be analyzed and provided in a separate clinical report at the end of the study. Data from roll-in cases will be included in the final safety analysis for the study.

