7.0 SUBJECT SELECTION

The following inclusion and exclusion criteria must be met for enrollment in the study:

Initial Inclusion Criteria (All must be answered YES for study eligibility.)

1. Subject is \geq 18 years of age.
2. Subject requires the creation of a vascular access graft for hemodialysis, secondary to a diagnosis of End Stage Renal Disease.
3. Subject is able to have the vascular access graft placed in an upper extremity.
4. Baseline imaging shows suitable vascular anatomy/ vessel size for the InterGraft™ Venous Connector and an artery at least 3.5 mm in diameter that is suitable for creating the arterial anastomosis.
5. Subject has a reasonable expectation of remaining on hemodialysis for at least 6 months.
6. Subject or his/her legal guardian understands the study and is willing and able to comply with the dialysis schedule and follow-up requirements.
7. Subject or his/her legal guardian provides written informed consent. NOTE: In accordance with the requirements of some Institutional Review Boards (IRB), where applicable, only those subjects with capacity to consent for themselves will be included. Thus, where required by the IRB, adult individuals who lack capacity to consent for themselves will be excluded from the study.

Final Inclusion Criterion to be applied at the time of surgery (Must be answered YES for enrollment into the study.)

8. Physician's examination at time of surgery shows no significant vessel lesions, calcification(s), anatomic structures or abnormalities that may limit ability to safely deploy the InterGraft™ Venous Connector or create a sutured arterial anastomosis.

Exclusion Criteria (All must be answered NO for study eligibility.)

1. Subject has a documented and unsuccessfully treated ipsilateral central venous stenosis as determined by imaging.
2. Subject currently has a known or suspected bacterial, fungal, or HIV infection. NOTE: Subjects with hepatitis B or C may be included in the study.
3. Subject has a known hypercoagulable or bleeding disorder or requires treatment with warfarin or heparin.

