9.0 SUBJECT SCREENING AND INFORMED CONSENT

Screening and Enrollment

All subjects referred for AVG implant should be screened for study eligibility. A member of the Research Team will evaluate the subject for eligibility. If all initial inclusion criteria are met and no exclusion criteria are present, a member of the Research Team should inform the subject about the study's purpose and should obtain written informed consent.

Final enrollment eligibility is determined at the time of surgery, after the physician has confirmed the final inclusion criterion is met. Enrolled subjects will be assigned a unique study subject identification number. Each study site will maintain screening and enrollment logs to record all subjects who were screened and all subjects who were enrolled. Reason for screen failures will be recorded. Screening log data will not be included in the primary database but will be reviewed during study monitoring.

No clinical site may contribute more than 25% of the total enrollment (excluding roll-in subjects).

Baseline Imaging

Angiographic or ultrasonic imaging of the target limb vasculature is routinely performed as part of determining the optimal AV access plan for a subject. As part of subject screening, baseline imaging should be reviewed to determine whether the subject meets the following criteria (as determined by the physician) for use of the VIG:

- General: Flow rate must be adequate for the creation of dialysis access, as previously mapped with ultrasound or angiography
- Vein inner diameter at planned anastomosis site is 4 -7 mm in luminal diameter
- Artery inner diameter at planned anastomosis site is at least 3.5 mm in luminal diameter

Informed Consent

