18.0 STATISTICAL ANALYSIS

Analysis population

The primary analysis population will include all subjects enrolled since June 5, 2018 and treated with the VIG + sutured arterial anastomosis, and also all VIG sub-study subjects enrolled after October 17, 2017. Such subjects who meet the enrollment criteria and in whom use of the VIG is attempted will be included in the intention-to-treat primary analysis population.

Data from roll-in subjects or from subjects included in the interim analysis population will not be included in the primary study analyses but these data will be analyzed and summarized separately. This includes subjects who previously received an AIG.

Choice of Performance Goal

Based on a review of the literature, prior studies of AVGs cleared for commercial distribution, and on observations from the first 52 enrolled subjects that received an AIG+VIG (e.g., the interim analysis population), the observed cumulative patency rate at 6 months for standard AVG implants ranged from 65% to 98% (Appendix B). Based on the proposed sample size for the current study (see below) and an expected cumulative patency rate of 84.6% for AVGs placed using the VIG, the exact, lower two-sided 95% confidence bound for cumulative patency is estimated to be 79.9%. A comparison to a target Performance Goal (PG) of 75% has been chosen for the evaluation.

Hypotheses

The primary study endpoint of the cumulative patency rate at 6 months will be evaluated in the following testable hypotheses:

$$H_0: (\text{Cumulative Patency Rate})_{6 \text{ Months}} \leq \text{PG}$$

$$H_1: (\text{Cumulative Patency Rate})_{6 \text{ Months}} > \text{PG}$$

where, PG = Performance Goal, here equal to 75%.

There are no formal hypotheses associated with the evaluation of secondary endpoints.

Data Analysis

General Statistical Considerations

- a. Descriptive statistics will be used to summarize subject baseline and outcome data collected during the study. Continuous variables will be summarized using means, standard deviations, medians, interquartile ranges, minimums and maximums. Categorical variables will be summarized in frequency distributions.
- b. Statistical analyses will be performed by validated software (e.g., SAS, SPSS, or Cytel Software)
- c. Copies of databases used to prepare clinical report summaries will be archived to enable any statistical analyses performed to be replicated.

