3.0 PROTOCOL

Enrollment in the study is determined at the time of surgery, after the physician has confirmed that inclusion criteria have been met, subjects have no exclusion criteria, and the final inclusion criterion has been met (e.g., target vessels are suitable for connection to a graft using the Venous InterGraft™ Connector and a sutured arterial anastomosis.) Enrolled subjects will be assigned a unique study subject identification number.

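### Roll-in status need only be set before enrollment, and enrollment is settled at surgery, so a compliant label can be chosen with the anatomy already in view

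*Protocol*

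**What the plan says.** **Label.** Protocol 17.0 (Roll-in Cases) states that roll-in "subjects will be identified as such before enrollment and treated according to the same protocol" and with the same 6-month follow-up as the main study.

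**Enrollment.** Protocol 9.0: "Final enrollment eligibility is determined at the time of surgery, after the physician has confirmed the final inclusion criterion is met". SAP 3.0 agrees: "Enrollment in the study is determined at the time of surgery, after the physician has confirmed that inclusion criteria have been met". The final criterion (Protocol 7.0, inclusion criterion 8) is an intra-operative look at the vessels: "Physician's examination at time of surgery shows no significant vessel lesions, calcification(s), anatomic structures or abnormalities that may limit ability to safely deploy".

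**Number and order.** Protocol 17.0 leaves the count open: "The number of roll-in cases per each site investigator will be determined by the Sponsor, in collaboration with the primary investigator at each site". It gives an expected size, which is not a binding limit: "No more than 1-2 roll-in cases per investigator are anticipated". On the order of cases at a site it says: "Upon successful completion of the roll-in case requirements, as determined by the Sponsor, sites will be permitted to begin enrollment in the main study". Protocol 6.0 and Table 2 cap roll-ins under the current plan at 15.

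**Analysis.** Protocol 18.0: "Data from roll-in subjects or from subjects included in the interim analysis population will not be included in the primary study analyses"; SAP 4.2 also excludes them. They are reported separately and count toward safety (Protocol 17.0). SAP 4.9 covers deaths, loss to follow-up and withdrawal, and has no analysis that adds roll-ins back.

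**The concern.** The trial has one arm and compares 6-month patency with a fixed goal of 75%. With no concurrent control, any selection into or out of the primary population passes straight into the estimate. Protocol 24.0 relies on an intention-to-treat primary analysis as a measure against bias, but a subject labelled roll-in never enters that population.

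The timing rule for the label should therefore come before anything that predicts outcome. Here it is tied to an event that follows inspection of the vein and artery. Anatomy can satisfy criterion 8 and still be difficult, and that is the information an operator would have when the label is still open. The point concerns what the wording permits; nothing in the documents suggests misuse.

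**Working it through.** **1. Timing.** Order of events under the text:

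- consent and initial criteria (Protocol 9.0);
- operating-room examination for criterion 8 (Protocol 7.0);
- enrollment settled (Protocol 9.0, SAP 3.0);
- use of the VIG.

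The label must precede the third step. Neither document requires it to precede the second. It always precedes the fourth, so it cannot depend on deployment or on later patency.

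**2. What the order rule leaves open.** Permission to begin the main study is given per site, but the number of roll-ins is set per investigator. Three openings remain:

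- an investigator who joins a site already enrolling;
- a site's early cases, while the number required can still be extended;
- the sponsor's own decision that the requirement is met.

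The counts do not settle who is a roll-in. Protocol 17.0 has roll-ins at each site and Protocol 6.0 allows up to 23 sites, yet Table 2 plans 0 to 15. Some sites may have met their requirement among the 25 earlier roll-ins in Table 3, but the text does not say which.

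**3. The plan's own sample size.** Exact one-sample binomial, goal 0.75, expected 0.846, one-sided 0.025. At n = 146 the test passes with 120 or more patent; the error rate is 0.0249 and power is 82.3%. The smallest n reaching 80% is 142. The stated 146 is reproduced closely enough, and 146 + 12 = 158. The labelling rule does not affect these numbers.

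**4. Possible size of the bias.** Inputs from the documents: 158 main-study subjects, up to 15 roll-ins, 173 in total (15/173 = 8.7%), goal 75%. Assumptions, not in the documents: patency over all 173 is exactly 75%, roll-ins have patency q, every subject's 6-month status is known, and SE(P) = √(P(1−P)/n).

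Pass line for Z = (P − 0.75)/SE(P) at n = 158: 129/158 = 0.816 gives Z = 2.16, and 128/158 gives Z = 1.93. The test passes at 129 or more. With no selection, P(X ≥ 129 | 158, 0.75) = 3.0%.

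Main-study rate if all 15 places are used selectively: (173 × 0.75 − 15q)/158 = (129.75 − 15q)/158.

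| q | Main-study rate | Chance of passing |
|---|---|---|
| 0.75 (no selection) | 0.750 | 3.0% |
| 0.65 | (129.75 − 9.75)/158 = 0.759 | 5.4% |
| 0.60 | (129.75 − 9.00)/158 = 0.764 | 7.0% |
| 0.50 | (129.75 − 7.50)/158 = 0.774 | 11.6% |

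Partial use, with the other roll-ins at 75%:

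- 3 at 50%: 3 × 0.50 + 12 × 0.75 = 10.5; (129.75 − 10.5)/158 = 0.755; chance 4.0%.
- 5 at 50%: 5 × 0.50 + 10 × 0.75 = 10.0; (129.75 − 10.0)/158 = 0.758; chance 4.9%.

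**5. Cross-check at n = 146 with the exact rule (120 or more).** The main-study rate is (161 × 0.75 − 15q)/146. For q = 0.65, 0.60 and 0.50 the chance of passing is 4.6%, 6.2% and 10.5%, against 2.5% without selection. The pattern is the same.

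**The case against.** The strongest reply is the order rule. A reader might infer from the timing gap that any site can move any difficult case out of the primary analysis at the table. The documents do not support that. As written, a site that has not completed its roll-in requirement has no main-study option, and a site that has completed it is in the main study. This largely stands. It confines the opening to an extendable number and to new investigators at active sites.

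Other limits also stand:

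- 1 to 2 roll-ins per investigator are expected, although this is not binding, and 15 is a ceiling.
- A subject who fails criterion 8 enters neither group, which limits how difficult a roll-in can be.
- Table 3 shows 30 of the 158 already enrolled by May 22, 2019; the new roll-in places cannot affect their selection. The arithmetic above does not change if those 30 also have 75% patency.
- Roll-ins have the same case report form and follow-up and are reported separately, so low patency among them would be visible.

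Separate reporting does not protect the primary estimate, however, and none of these limits places the label before the vessel examination.

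**Conclusion.** The timing gap is real, and neither document closes it. It is a modest weakness that should be corrected. It does not invalidate the primary analysis.

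The 5-12% range is an upper bound. It needs all 15 places filled with subjects at 50-65% patency and overall patency exactly at the goal; those patency rates are assumed. Under smaller selective use (3 to 5 subjects at 50%) the chance of passing is 4.0-4.9% against 3.0%, and if roll-ins resemble main-study subjects the bias is zero.

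A reader might also infer that adding roll-ins back would overturn a result at the planned rate. It would not under plausible values. With 84.6% in 158 and an assumed 60% in 15, the pooled rate is (158 × 0.846 + 15 × 0.60)/173 = 82.5%. At n = 173 the pass line is 140/173 = 80.9%, and 82.5% gives Z of about 2.6.

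**What to change.** **Protocol 17.0.** Replace the present timing rule with the following:

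- Roll-ins are the first k cases of each investigator in which the VIG is attempted.
- The sponsor sets k before that investigator's first case.
- Each subject's label is recorded with date and time before entry to the operating room.
- Any later increase in k is documented before the next subject is identified, and applies only to the next consecutive cases.

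Counting attempted cases matters because a consented subject can fail criterion 8 at surgery and never be enrolled. Counting consents could use up k with no training case performed. Recording the label before the operating room also adds no new requirement on when consent is taken.

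**SAP 4.9.** Add one sensitivity analysis that repeats the primary Kaplan-Meier estimate with the current-plan roll-ins (VIG plus sutured arterial anastomosis) included.

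**Cost.** Wording in two documents, one log entry per subject and one extra run on data already collected. The sample size is unchanged. The sponsor loses some freedom to add roll-ins case by case, and the sensitivity estimate may be slightly less favourable than the primary one.

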18.0 STATISTICAL ANALYSIS

Analysis population

The primary analysis population will include all subjects enrolled since June 5, 2018 and treated with the VIG + sutured arterial anastomosis, and also all VIG sub-study subjects enrolled after October 17, 2017. Such subjects who meet the enrollment criteria and in whom use of the VIG is attempted will be included in the intention-to-treat primary analysis population.

Data from roll-in subjects or from subjects included in the interim analysis population will not be included in the primary study analyses but these data will be analyzed and summarized separately. This includes subjects who previously received an AIG.

Choice of Performance Goal

Based on a review of the literature, prior studies of AVGs cleared for commercial distribution, and on observations from the first 52 enrolled subjects that received an AIG+VIG (e.g., the interim analysis population), the observed cumulative patency rate at 6 months for standard AVG implants ranged from 65% to 98% (Appendix B). Based on the proposed sample size for the current study (see below) and an expected cumulative patency rate of 84.6% for AVGs placed using the VIG, the exact, lower two-sided 95% confidence bound for cumulative patency is estimated to be 79.9%. A comparison to a target Performance Goal (PG) of 75% has been chosen for the evaluation.

Hypotheses

The primary study endpoint of the cumulative patency rate at 6 months will be evaluated in the following testable hypotheses:

$$H_0: (\text{Cumulative Patency Rate})_{6 \text{ Months}} \leq \text{PG}$$

$$H_1: (\text{Cumulative Patency Rate})_{6 \text{ Months}} > \text{PG}$$

where, PG = Performance Goal, here equal to 75%.

There are no formal hypotheses associated with the evaluation of secondary endpoints.

Data Analysis

General Statistical Considerations

- a. Descriptive statistics will be used to summarize subject baseline and outcome data collected during the study. Continuous variables will be summarized using means, standard deviations, medians, interquartile ranges, minimums and maximums. Categorical variables will be summarized in frequency distributions.
- b. Statistical analyses will be performed by validated software (e.g., SAS, SPSS, or Cytel Software)
- c. Copies of databases used to prepare clinical report summaries will be archived to enable any statistical analyses performed to be replicated.
- d. A full data listing will be prepared, including an electronic version in a standard computer-accessible format (e.g., SAS) at the completion of the study. Listings of data represented on the CRF will be provided for all key baseline, demographic and outcome variables to facilitate further investigation of tabulated values and to allow for clinical review of safety variables.

A one-sided p-value of 0.025 will be considered evidence of statistical significance for the primary study endpoint.

Primary Endpoint

Cumulative patency at 6 months will be evaluated using the estimated patency from a Kaplan Meier survival analysis. The test statistic will take the following form:

$$\text{Z-test statistic} = (P - 0.75) / \text{SE}(P)$$

Where, (P) represents the Kaplan Meier estimate of cumulative patency at 6 months, and the standard error SE (P) is estimated using the method of Peto *et al* (1977).²⁴

Subjects who withdrawn for reasons other than loss of cumulative patency will be included in the analysis up until the time of withdrawal, and be considered censored in the analysis, according to usual convention, after withdrawal.

Secondary Endpoints

The following secondary endpoints will be evaluated in the study, but there are no formal hypotheses that are tested or associated significance levels assigned to results. Nominal confidence intervals may be calculated in summarizing clinical results for secondary endpoints but not for purposes of product labeling.

1. Acute device success will be summarized by the success rate and associated 95% confidence interval.
2. Primary Unassisted Patency at 6 Months will be summarized by the patency rate and associated 95% confidence interval.
3. Time-to-First-Cannulation will be summarized by the median time and frequency distribution.
4. Number and type of interventions required to maintain secondary patency will be summarized by the frequency distributions of numbers and types of interventions.
5. Number and type of serious adverse events (SAEs) will be summarized by frequency distributions of the numbers and types of SAEs, the subject rates of SAEs by type, and the proportion of subjects with at least one SAE.

Additional Safety Data

In addition to summarizing and reporting SAEs (Secondary Endpoint 5), the number and type of non-serious adverse events (AEs) will be summarized by frequency distributions of the numbers and types of AEs and the subject rates of AEs by type.

Gender Analysis

Cumulative patency rates between genders will be compared by gender using a log rank test statistic to compare their respective Kaplan-Meier survival curves. The heterogeneity of cumulative patency rates will also be examined using the test statistic used for the primary endpoint analysis. Gender specific summary statistics will also be provided for study primary and secondary endpoints.

Pooling of Sites

Cumulative patency rates will be compared between study sites using a Chi-square test to evaluate the association between rates and sites. A p-value of 0.15 or less will be considered evidence of a possible site interaction, requiring a further evaluation of subject baseline factors to determine if site differences can be explained by these factors.

Sample Size Justification and Planned Enrollment

Sample size adjustment recommendations from the planned interim analysis subject data have been considered in determining the sample size for the current study. The required sample size for the study was estimated using the following assumptions:

- Test basis: Kaplan-Meier estimate of cumulative patency rate at 6 months, with exact binomial estimation for purposes of sample size
- Type I error (alpha): 0.025 (one-sided)
- Statistical power: 80%
- Performance Goal (PG): 75%
- Expected cumulative patency for InterGraft at 6 months: 84.6%.

Based on the above assumptions, a total of 146 evaluable subjects will be required to compare observed cumulative patency to a PG of 75%. With an expected loss-to-follow-up rate of 8% over 6 months (e.g., 12 subjects), a total of 158 evaluable subjects will be enrolled into the main study, defined as primary analysis population of 146 subjects plus allowance for 12 subjects lost-to-follow up. Planned minimum and maximum enrollment under the current investigational plan is summarized in **Table 2**.

Table 2: Planned Enrollment in the Current Investigational Plan

Study Group	Minimum enrollment	Maximum enrollment
Roll-in	0	15
Primary analysis	146	146
Allowance for subjects lost-to- follow up	12	12
TOTAL	158	173

Planned enrollment under the entire study conducted under IDE G140221 is summarized in **Table 3**. This includes all subjects previously enrolled under the approved IDE G140221.

Table 3: Summary of Planned Enrollment under IDE G140221, as of May 22, 2019

Study Group	Maximum enrollment (or actual enrollment if known)
Roll-in subjects enrolled prior to May 22, 2019 (includes USA + Mexico Sites)	25 (actual enrollment)
Current Investigational Plan: Roll-in subjects	up to 15
Current Investigational Plan: subjects previously enrolled and to be included under the current investigational plan	30 (actual enrollment)
Current investigational plan: new subjects remaining to be enrolled after May 22, 2019 (Primary analysis + allowance for lost-to-follow up)	128
Previously enrolled subjects that received VIG+ AIG (includes USA + Mexico sites, does not include roll-in cases)	68 (actual enrollment)
Previously enrolled subjects in VIG sub-study that are not included under the current Investigational Plan, but were included in the interim analysis)	7 (actual enrollment)
TOTAL	273

